Study name: Local anesthetic for plateau fractures

Clinicaltrials.gov identifier

June 3 2024

Local anesthetic for plateau fractures

[name] MD

Introduction

Tibial plateau surgical fixation of fractures is painful to patients and often extends their hospital stay for pain management. If the application of a local anesthetic into the joint at the time of surgery can reduce post-operative pain this will be a direct benefit to patients. There is no agreed upon single standard of care. There are multiple different pain management strategies for dealing with post-operative pain. The goal of this study is to determine if this specific treatment can become standard of care. Preliminary work has reviewed existing cases in both arms verifying that there are no safety concerns.

Methods:

Inclusion Criteria

18 years or older

Tibial plateau fracture treated with ORIF

Exclusion Criteria

Known allergy to Bupivacaine

Data Points

Age

Hospital length of stay

Randomized arm

Pain at time of discharge

Pain at time of 1st follow-up

Methodology

Patients will be enrolled at a single facility (Harborview Medical Center-HMC). Patients who meet inclusion criteria will be assigned to one of two groups based on randomization. Both treatments are considered acceptable standards of practice in the orthopedic trauma community on a local and national level. All patients will be treated similarly until the time of local anesthetic application. One group will receive bupivacaine injection into the joint the other group will receive saline.

Risks:

There is no known risk to the patient as both treatments are current standard of practice both nationally and locally. All patient identifiers will be kept private. All data will be stored on a password protected database available only to the study team.

Benefits

The study performed will provide information regarding the optimal treatment strategy for post-operative pain reduction in proximal tibial plateau fractures. The information is of benefit to patients when being counseled by surgeons regarding their hospital length of stay and pain medication needs.

Procedure to ensure confidentiality

No patient identifiers will be used during the formal study. Identifiers such as name and medical record numbers will be used to identify patients with a tibial plateau fracture and will be stored on a password protected departmental network in a master file. Data files will be listed with a subject number.

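### Age is the only baseline characteristic in Data Points, so a trial run to that list could adjust its pain comparisons, and describe its arms, on age alone

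*Protocol*

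**What the plan says.** The Data Points section of the protocol has five entries: age, length of stay, randomized arm, "Pain at time of discharge" and "Pain at time of 1st follow-up". The protocol names no other variable for collection, and it does not say that the list is complete.

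Eligibility is broad. Besides adult age, the inclusion criterion is "Tibial plateau fracture treated with ORIF", and the only exclusion is "Known allergy to Bupivacaine". Neither criterion restricts fracture severity or additional injuries.

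On allocation, the Methodology section states: "Patients who meet inclusion criteria will be assigned to one of two groups based on randomization". It names no stratification factor. On care before the intervention it states: "All patients will be treated similarly until the time of local anesthetic application". The Introduction places the injection at the time of surgery.

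The section on confidentiality says that names and medical record numbers serve to identify patients and "will be stored on a password protected departmental network in a master file".

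**The concern.** Two of the three listed outcomes are pain scores, yet no pain score from before treatment is listed. Nor is there any item on injury burden, although eligibility leaves room for patients with very different injuries.

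Which variables are collected is settled in the protocol. A SAP chooses among recorded variables and cannot adjust for one that was never recorded, so this is not simply a detail deferred to a document that is not shown.

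Two things are at stake:

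- **Precision.** A pain score recorded before randomization cannot be affected by the assigned arm. If it predicts later pain, adjusting for it narrows the interval around the treatment difference.
- **Transparency.** With age alone, the report could not show whether chance had put patients with more pain or more injuries into one arm.

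**Working it through.** **Step 1. Class the listed items by timing.**

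| Item | Class |
|---|---|
| Age | baseline characteristic |
| Randomized arm | assignment |
| Length of stay | outcome after randomization |
| Pain at discharge | outcome after the injection |
| Pain at first follow-up | outcome after the injection |

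The count is one baseline characteristic, one assignment and three outcomes. There are no items on baseline pain and none on injury burden.

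**Step 2. Inputs for the size.** The protocol gives no sample size, standard deviation, effect size or correlation, so there is no figure of its own to reproduce. All inputs below are assumptions:

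- N, the total number of patients, is 40, 100 or 200.
- R2 is the share of the pain variance left after age that the two added items (pain before randomization; isolated fracture or additional injuries) jointly explain. It is set at 1%, 9% or 25%.
- The pain score is treated as roughly continuous. The figures do not apply to length of stay.

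**Step 3. Formula.** In a two-arm analysis of covariance with k covariates, the variance of the adjusted arm difference is proportional to

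(1 - R2_k) × (N - 3)/(N - k - 3),

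where R2_k is the share of variance that the k covariates explain. The second factor is the cost of estimating their coefficients. Going from k = 1 (age) to k = 3 (age and the two added items), the ratio of variances is

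(1 - R2) × (N - 4)/(N - 6).

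A ratio below 1 is a gain. Setting it equal to 1 gives the break-even value R2 = 2/(N - 4).

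**Step 4. Numbers.**

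| N | (N - 4)/(N - 6) | R2 = 1% | R2 = 9% | R2 = 25% | Break-even R2 |
|---|---|---|---|---|---|
| 40 | 36/34 = 1.0588 | 1.048 (+4.8%) | 0.964 (-3.6%) | 0.794 (-20.6%) | 2/36 = 5.6% |
| 100 | 96/94 = 1.0213 | 1.011 (+1.1%) | 0.929 (-7.1%) | 0.766 (-23.4%) | 2/96 = 2.1% |
| 200 | 196/194 = 1.0103 | 1.000 (0.0%) | 0.919 (-8.1%) | 0.758 (-24.2%) | 2/196 = 1.0% |

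**Step 5. On the scale of the standard error.** Taking square roots at N = 40, √1.048 = 1.024 and √0.794 = 0.891, so the standard error would be about 2% larger at worst and about 11% smaller at best. At N = 100, √1.011 = 1.006 and √0.766 = 0.875, so it would be about 1% larger to about 12% smaller.

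**The case against.** The strongest reply is that nothing here is an error. Randomization protects the comparison, the list is not declared closed, and record numbers are kept, so chart data could be retrieved later. If a pain score from before surgery is in the chart, leaving it off the list does not destroy it; if it is not, listing it does not create it. Every input to the size is assumed, and over the range shown even the direction is open. The upper R2 may also be optimistic for an unstandardized chart score and a two-way injury split.

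Most of this stands, and it makes the point an optional improvement. It does not remove the point. The protocol describes the master file as a means of identifying patients and does not provide for drawing baseline data from it. Covariates chosen after outcomes are known also carry less weight than covariates named beforehand.

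A reader might infer three stronger things, none of which the document supports:

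- **That the arm comparison is biased or confounded.** It is not: assignment is by randomization, and an unadjusted comparison is valid.
- **That no analysis could ever use more than age.** This follows only if the list is treated as complete, which the protocol does not say.
- **That prior opioid use must also be recorded, because the Benefits section speaks of "hospital length of stay and pain medication needs".** A baseline yes/no field would not supply the medication use after surgery that the phrase suggests. Without a place in the adjustment, it would add nothing to precision either.

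It is also fair to say that the model for length of stay and the handling of missing baseline values belong in the SAP. Their absence here is no fault.

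**Conclusion.** The point holds as a low-cost improvement to consider. If Data Points is followed as written, age is the only characteristic on which the pain comparisons can be adjusted and the arms described. The cost is in precision and in the ability to show chance imbalance; validity is not affected.

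The size cannot be fixed from the protocol. Under the assumptions above, adding the two items does anything from slight harm in a small trial with weak covariates to a reduction of between a fifth and a quarter in the variance when R2 is 25%. Nothing in the document shows where in that range this trial would fall. The break-even values show how little the items need to explain to pay for themselves: 5.6% with 40 patients and 2.1% with 100.

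**What to change.** Add two entries to Data Points, both taken from the medical record where available:

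1. the last pain score recorded before randomization;
2. isolated tibial plateau fracture or additional injuries.

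State in the protocol or SAP, before any outcome data are seen, that the pain comparisons adjust for age and these two items. Report both by arm with age in the baseline table. Eligibility does not change. Leave the length-of-stay model and the rule for missing baseline values to the SAP.

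The cost is two abstracted fields and one sentence, with no extra patients, visits or procedures. That the values are in the record is an assumption, since the protocol does not say so, and some will probably be missing. If the items predict little and the trial is small, precision falls slightly (about 5% more variance at N = 40 with R2 = 1%).

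### Does the protocol need to state who is masked, given that controls receive saline and every listed outcome is completed after the injection?

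*Protocol*

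**What the plan says.** The Methodology section assigns patients to two groups by randomization and defines the groups in one sentence: "One group will receive bupivacaine injection into the joint the other group will receive saline". The Introduction places the injection at the time of surgery. Methodology also says of the two options: "Both treatments are considered acceptable standards of practice in the orthopedic trauma community on a local and national level". It promises similar handling of all patients up to the injection and is silent on handling afterwards.

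The Data Points list has five entries: age, "Hospital length of stay", "Randomized arm", "Pain at time of discharge" and "Pain at time of 1st follow-up". The protocol does not call any of them an outcome, but once age and arm are set aside the other three are the only candidates.

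On data handling, the Risks section says: "All data will be stored on a password protected database available only to the study team". The confidentiality section adds that files carry a subject number. The words blind, mask and placebo do not appear, and nothing is said about who prepares the injection or who may see the allocation.

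**The concern.** Pain is presumably reported by the patient, and length of stay ends with a decision by staff. Both can shift when the arm is known. The protocol itself ties the two together in the Introduction: "Tibial plateau surgical fixation of fractures is painful to patients and often extends their hospital stay for pain management". If patients, the ward or the pain recorder knew the arm, expectation could colour the pain scores and influence when patients are sent home, and no listed outcome would be immune. The stated aim is to decide whether the treatment can become standard of care, which needs a fair comparison.

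The gap also cannot be set aside as something for the statistical analysis plan. Masking happens in theatre and on the ward, before any analysis, and an analysis plan cannot mask a patient who has already been told the arm. Read literally, a site could follow every sentence of the protocol and still run the trial open-label.

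**Working it through.** The protocol gives no sample size, effect size, standard deviation or error rate, so no bias can be calculated. The check is a reading of the whole text, asking of each relevant statement what it shows about knowledge of the arm.

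1. **Any direct statement on masking.** None was found, either for or against.

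2. **The comparator.** Controls receive saline. The sentence does not give its route, but its parallel form reads as a second injection into the joint. An inert injection in place of no injection is normally chosen so that the arms look alike. This points towards concealment without proving it.

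3. **The description of both options as accepted practice ("Both treatments are considered acceptable standards of practice in the orthopedic trauma community on a local and national level").** This concerns acceptability. It neither says nor implies that anyone is told which option was given, so it does not cancel the inference in step 2.

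4. **The arm as a data point ("Randomized arm").** Every randomized trial must record the arm. Listing it does not show when it is entered or who sees it.

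5. **The database sentence ("All data will be stored on a password protected database available only to the study team").** This is a privacy safeguard. It does not say whether the person recording pain belongs to the study team, or whether the arm can be seen before pain is recorded.

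6. **Similar treatment up to the injection.** This marks the point where the arms diverge. It does not announce that later care or assessment will differ.

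7. **The count of exposed outcomes.** Of 5 data points, 2 (age and arm) are not outcomes, leaving 5 − 2 = 3. All 3 are completed after the injection; length of stay may begin before surgery but is fixed at discharge. The count is correct, but outcomes follow treatment in practically every treatment trial. It shows what would be exposed if the arm were known, not that the arm is known.

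Taken together, the text holds no statement that anyone is unmasked, one design feature that suggests masking, and several sentences that do not bear on the question.

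**The case for a change.** The strongest case for asking for a change is that masking belongs in a protocol, that saline secures no concealment unless someone prepares and labels it so that the arm stays hidden, and that a few sentences would put the matter beyond doubt. The textual basis is sound: the available protocol does not say who is masked, and with pain as the main interest the question is a natural one.

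What stands is that the detail is absent from the text at hand and that asking about it is sensible. What does not stand is the step from silence to a flaw. If masking is already practised or described in the consent form, writing it down would be enough, so the complaint concerns documentation and not a wrong design choice.

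A fuller remedy would also go beyond what the protocol supports. A rule on syringe preparation would need someone uninvolved in later care, and the protocol does not identify such a person. The surgeon's own status would still have to be settled. A blanket statement that care never depends on the arm would clash with any provision for emergency unmasking, whose purpose is to let care take account of the arm.

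**Conclusion.** No change to the plan follows. The observation is accurate: the available protocol does not name who is masked, and all three outcome-type data points are completed after the injection. But nothing in it is misstated or contradictory, and nothing shows that the trial is run with the arm known. The saline control permits masking and suggests that it is intended, and a site team would ordinarily use it that way. Any bias is conditional on the arm being known, and its size and direction cannot be estimated from the document.

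This rests on two assumptions: that the saline is injected in the same manner as the bupivacaine, which the sentence implies but does not spell out, and that pages outside the available text may state the masking. If the investigator confirmed that patients or pain recorders are told the arm, the point would have to be reopened. Short of that, it is a question for the investigator and not a defect in the plan.
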